TDR	Total Diet Replacement
GIG	Governance and implementation Group

STUDY SYNOPSIS

[figure not shown]
Title of Study:	Diabetes REmission Clinical Trial-Aus; DiRECT-Aus
Study Centre:	University of Sydney
Duration of Study:	Active intervention: 12 month per subject Follow up: 4 years after completion of active intervention
Primary Objective:	
To determine whether a program, designed to achieve remission of T2DM to normal glucose tolerance by substantial weight loss using a very low energy diet (VLED), can be effectively delivered within the routine primary care setting where most people with T2DM are managed in Australia.
 
The Diabetes Remission Clinical Trial (DiRECT) was a study funded by Diabetes UK that tested whether a low calorie-based weight management program, delivered in primary care could result in long term Type 2 diabetes remission. Diabetes UK, the University of Glasgow and Newcastle University have since developed the DiRECT principles, which set out the core elements of health intervention to have the best chance of replicating the outcomes of the DiRECT study.
 
This project intent is to replicate or better the remission results achieved in the UK DiRECT study for people with T2DM in the participating PHN regions and undertaking the intervention in general practice.

Secondary Objective:	To evaluate the attitudes of participants to the VLED program including acceptability, ease of use and perceived value.
Primary Endpoint:	% of participants achieving a non-diabetic HbA1c (<6.5%; <48 mmol/mol) at 12 months having ceased all diabetes medication for at least the preceding 2 months
Rationale:	Bariatric surgery can convert 70-80% of people with T2DM to the non-diabetic state. The DiRECT trial provided evidence that T2DM could also be reversed by a strict energy restricted diet, with 10-15kg weight loss. The present study will determine if the results of the DiRECT trial can be replicated in an Australian primary care setting and establish whether it is possible to produce remission of T2DM at 12 months and sustain it over 5 years. An VLED can be provided relatively cheaply in the primary care setting where obesity and T2DM are managed, using a total diet replacement (TDR), such as Optifast, which is readily available to the Australian general public. The study will also assess quality of life and attitudes of subjects during the intervention.

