3.2 Inclusion criteria

- Written informed consent
- Men and women aged 20-65 years, all ethnicities
- T2DM of duration 0-6 years (diagnosis based on Australian diagnostic criteria)
- HbA1c criteria at study entry:
 - 48 mmol/mol ($\geq 6.5\%$) **or**
 - HbA1c > 42 mmol/mol (6%), but < 48 mmol/mol (6.5%) if subject is taking blood glucose lowering medication(s)
- Body Mass Index (BMI) >27 kg/m²
- Women of childbearing potential must be ready and able to use highly effective methods of birth control that result in a low failure rate of less than 1% per year when used consistently and correctly, unless truly abstinent (as a lifestyle choice), in a committed relationship with a male who is medically sterile or exclusively same sex attracted.

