4.2.2 Management of blood glucose lowering and blood pressure lowering medications

Hypoglycaemic agents will be withdrawn on commencement of the VLED. Patients will be educated on detecting deteriorating glycaemia and glycaemia will be measured at each visit using capillary blood glucose measurement. HbA1c will also be measured 3-monthly. If capillary blood glucose is >15mmol/L or HbA1c >9% or >1% change in HbA1c from previous measurement, the GP will consider re-introducing oral hypoglycaemic medication. Recommencement of medication due to elevated blood glucose will be captured in the medication log and the reason noted.

Hyperglycaemia will also be recorded as an adverse event (see section 5).

Blood pressure will be measured at each visit during the first 12 months of the study. Subjects will be asked about symptoms of postural hypotension. If blood pressure is <110/60 mmHg, blood pressure medication will be reviewed and the medication will either be withdrawn or the dose reduced. If blood pressure is >140/90, prescription of blood pressure lowering medication will be considered by the GP.

All changes to blood glucose lowering and blood pressure lowering medications will be recorded on the medications CRF.

Other medications will be maintained, and their continued need and dosage reviewed as part of routine care.

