5.1 Adverse Event Monitoring

Adverse events

Adverse events are defined as any new medical event or worsening of an existing condition (including a clinically significant laboratory result) with onset after the signing of consent, whether or not the adverse event is deemed related to the study procedures. Participants will be questioned regarding the onset of any adverse events at each appointment in a non leading way (e.g how are you feeling). Participants will also be encouraged at the start of the study to spontaneously report any changes they notice while on the study. The following information will be recorded:

Adverse event term

Note: This should be a diagnosis of the event based on signs, symptoms, and/or other clinical information. In the absence of a diagnosis, the individual signs/symptoms should be documented

- Start date
- Status (resolved/recovered, resolving/recovering, not resolved/recovered, resolved/recovered with sequelae)
- End Date
- Seriousness (serious or not serious)
- Severity (mild, moderate or severe based on impact to daily functioning)
- Relationship to study treatment (definitely related, likely related, possibly related, unlikely related, not related)
- Treatment required (medication, other, none)
- Action taken with study treatment (no change in study treatment, study treatment modified, study treatment stopped)

The adverse events information may be collected and recorded by the dietitian/nurse. If the dietitian/nurse is unsure regarding relatedness and action to be taken with study procedures, they must consult the GP. If the adverse event requires treatment, this must be prescribed by the GP or another appropriately qualified health care professional.

Glycaemia and blood pressure adverse events

Hyper- and hypoglycaemia and low and high blood pressure will be recorded as adverse events using the criteria below:

Hyperglycaemia

Capillary blood glucose >15 mmol/L or HbA1c >9% or >1% change in HbA1c from previous measurement

Hypoglycaemia

Capillary blood glucose < 4 mmol/L

Low blood pressure

Systolic < 110 or diastolic <60

High blood pressure

Systolic >140 or diastolic > 90

Serious Adverse Events

Serious adverse events (SAE) are those which meet any of the following criteria:

- Results in death
- Is life threatening.

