APPENDIX A: DiRECT-Aus SCHEDULE OF ASSESSMENTS

		Total Diet Replacement Phase								Food Reintroduction Phase		
Appointment		1	2	3	4	5	6	7	8	9	10	11
Week		-2	0	1	3	5	7	9	11	13	15	17
Study Procedure	Responsibility											
Review & discuss study participation	GP/nurse/dietitian	√										
Obtain Informed Consent	GP/nurse/dietitian	√										
Review Inclusion/Exclusion Criteria	GP	√										
Collect medical history	GP/nurse/dietitian	√										
Record medications	GP/nurse/dietitian	√	√	√	√	√	√	√	√	√	√	√
Height	Nurse/dietitian	√										
Weight	Nurse/dietitian	√	√	√	√	√	√	√	√	√	√	√
Waist Circumference	Nurse/dietitian	√	√	√	√	√	√	√	√	√	√	√
Hip Circumference	Nurse/dietitian	√										
Blood Pressure	Nurse/dietitian	√	√	√ ^a	√ ^a	√ ^a	√ ^a	√ ^a	√ ^a	√ ^a	√ ^a	√ ^a
Blood & urine samples	Pathology	√										
Hypoglycemic agents discontinued	Nurse/dietitian ^b		√									
Capillary blood glucose	Nurse/dietitian		√	√ ^c	√ ^c	√ ^c	√ ^c	√ ^c	√ ^c	√ ^c	√ ^c	√ ^c
Repeat HbA1c	Pathology									√		
EQ-5D questionnaire	Participant		√							√		
Binge Eating Questionnaire	Participant		√							√		
Food Acceptability Questionnaire	Participant		√							√		
Baecke Physical Activity	Participant		√							√		
Record steps previous two weeks	Nurse/dietitian		√ ^c							√		
Urine pregnancy test	Nurse/dietitian	√										
Adverse events monitoring	Nurse/dietitian		√	√	√	√	√	√	√	√	√	√

Schedule of Assessments (continued)

		Weight Maintenance Phase (Year 1)									
Visit		12	13	1	15	16	17	18	19	20	
Week		21	25	29	33	37	41	45	49	0+52	
Study Procedure											
Record medications		√	√	√	√	√	√	√	√	√	
Height										√	
Weight		√	√	√	√	√	√	√	√	√	
Waist Circumference		√	√	√	√	√	√	√	√	√	
Hip Circumference										√	
Blood Pressure		√ ^a	√ ^a	√ ^a	√ ^a	√ ^a	√ ^a	√ ^a	√ ^a	√ ^a	
Blood & urine samples										√	
Capillary blood glucose		√ ^c	√ ^c	√ ^c	√ ^c	√ ^c	√ ^c	√ ^c	√ ^c	√ ^c	
HbA1c			√			√				√	
EQ-5D questionnaire										√	
Binge eating scale										√	
Food Acceptability Quest.										√	
Baecke Physical Activity										√	
Record steps previous two weeks										√	
Urine pregnancy test										√	
Adverse event monitoring		√	√	√	√	√	√	√	√	√	

^a Blood pressure medication reduced if BP <110/60 mmHg or reintroduced if BP subsequently >140/90 mmHg

^b GP to make medication adjustment if capillary blood glucose > 15mmol/L

^c hypoglycaemic agents reintroduced if capillary blood glucose >15 mmol/L or HbA1c >9% or >1% change from last measurement

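### The HbA1c limb of the hyperglycaemia criterion has no direction, so a literal reading codes a large fall as an adverse event; separately, Appendix A and the body text disagree on whether drug reintroduction is automatic

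*Protocol*

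**What the plan says.** Three places in the protocol use the same HbA1c criterion.

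- **Section 5.1, hyperglycaemia:** "Capillary blood glucose >15 mmol/L or HbA1c >9% or >1% change in HbA1c from previous measurement". The instruction above it is that "Hyper- and hypoglycaemia and low and high blood pressure will be recorded as adverse events using the criteria below". The same section lets the dietitian or nurse collect and record adverse events, and defines an adverse event in general as "any new medical event or worsening of an existing condition".
- **Section 4.2.2:** when the same three limbs are met, "the GP will consider re-introducing oral hypoglycaemic medication". It adds: "Recommencement of medication due to elevated blood glucose will be captured in the medication log and the reason noted".
- **Appendix A, footnote c:** "hypoglycaemic agents reintroduced if capillary blood glucose >15 mmol/L or HbA1c >9% or >1% change from last measurement".

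Section 4.6 also bears on the drug decision. It makes the GP the person who decides on reintroducing glucose-lowering medication, if it is needed.

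The primary endpoint in the Study Synopsis is HbA1c below 6.5% at 12 months, "having ceased all diabetes medication for at least the preceding 2 months".

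**The concern.** There are two separate defects.

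**Direction.** The programme aims to lower HbA1c below 6.5%. A criterion that fires on any change of more than 1% also fires on a large fall, which is the result the programme seeks. If it is coded as written, some successes enter the safety data as hyperglycaemia, and the hyperglycaemia count can no longer be interpreted. The limb also does not say whether 1% means one HbA1c percentage point or 1% of the previous value.

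**Discretion.** Footnote c reads as an automatic restart, whereas Sections 4.2.2 and 4.6 leave the decision to the GP. Being off diabetes drugs is one of the two conditions for remission, so the restart rule can affect the primary endpoint. Practices working from the schedule table and practices working from the body text could act differently. The Study Synopsis plans 25 practices, in a study whose result is to be judged against the UK trial.

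**Working it through.** The protocol gives no figure to reproduce on this point. The check is a comparison of the text plus three short calculations.

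**1. Direction of each limb in Section 5.1**

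| Criterion | Limb | Direction stated |
|---|---|---|
| Hyperglycaemia | capillary glucose >15 mmol/L | yes |
| Hyperglycaemia | HbA1c >9% | yes |
| Hyperglycaemia | HbA1c change >1% | **no** |
| Hypoglycaemia | capillary glucose <4 mmol/L | yes |
| Low blood pressure | systolic <110, diastolic <60 | yes |
| High blood pressure | systolic >140, diastolic >90 | yes |

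Only the HbA1c change limb lacks a direction.

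**2. Which responders a literal reading catches**

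Inputs: entry HbA1c is at least 6.5%, or "HbA1c > 42 mmol/mol (6%), but < 48 mmol/mol (6.5%) if subject is taking blood glucose lowering medication(s") (Section 3.2), and must be below 10% (Section 3.3). Remission needs a value below 6.5%, so 6.4% is used as the target. HbA1c is measured at screening and at weeks 13, 25, 37 and 52 (Section 4.4, Table 1). Here 1% is read as one percentage point.

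Fall in one interval = baseline − 6.4. The limb fires if this exceeds 1.0.

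- 7.0 − 6.4 = 0.6: does not fire
- 7.4 − 6.4 = 1.0: does not fire
- 7.5 − 6.4 = 1.1: fires
- 8.0 − 6.4 = 1.6: fires
- 9.0 − 6.4 = 2.6: fires

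A participant who reaches 6.4% in a single interval is therefore caught from a baseline of about 7.5% up to just under 10%. Responders who start lower and just reach the target, or whose fall is spread over several intervals, may not be caught.

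The scale matters too. If 1% were relative, the threshold at 8.0% would be 0.01 × 8.0 = 0.08 points, and almost any change would fire.

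**3. Worst-case size at week 13**

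The protocol gives no mean or SD for the HbA1c change. Assume a normal distribution of falls with mean m of 0.6 to 1.2 points and SD s of 0.8 to 1.3. Then P(fall > 1) = 1 − Φ((1 − m)/s).

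- m = 0.6, s = 0.8: 1 − Φ(0.50) = 31%
- m = 0.6, s = 1.3: 1 − Φ(0.31) = 38%
- m = 1.2, s = 0.8: 1 − Φ(−0.25) = 60%
- m = 1.2, s = 1.3: 1 − Φ(−0.15) = 56%

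With 250 participants, the range of 31% to 60% is about 77 to 150 records. Widening the assumed means to 0.5 to 1.5 points (SD 0.8 to 1.2) gives 27% to 73%. Both ranges require every participant to have a week 13 value and every such fall to be coded literally.

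**4. When a restart costs remission**

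Taking a month as 30.4 days, the two-month drug-free window opens at 52 − (2 × 30.4)/7 = week 43.3. The interval from each earlier HbA1c test to that point is:

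- week 13: 43.3 − 13 = 30.3 weeks
- week 25: 43.3 − 25 = 18.3 weeks
- week 37: 43.3 − 37 = 6.3 weeks

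A drug restarted after one of these tests and stopped again before about week 43 leaves the endpoint attainable. A drug still being taken after that point makes the participant a non-remitter whatever the HbA1c. Section 4.2.2 does not say when a reintroduced drug would be stopped.

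**The case against.** The strongest reply is that no clinician would misread the rule. The limb sits under a hyperglycaemia heading, the general definition of an adverse event speaks of worsening, and Section 4.2.2 introduces the rule with patient education on deteriorating control and ties a restart to raised glucose. The body text also gives the restart decision to the GP consistently, so footnote c can be seen as table shorthand.

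Most of this stands. A rise is probably what was meant, and a GP is unlikely to restart drugs in someone whose HbA1c has just reached the remission range. It does not remove the defect, because Section 5.1 tells staff to record these events by the listed criteria, and the recorder may be a dietitian or nurse. Footnote c, as worded, still contradicts the body text.

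A reader might also infer three stronger conclusions that the protocol does not support:

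- **That the rule by itself defeats the primary endpoint.** A restart costs remission only if the drug is still taken in the last two months, and a restart after the week 52 test cannot undo that result.
- **That a fall in HbA1c triggers reintroduction.** Only footnote c reads as automatic.
- **That the hyperglycaemia count is a main safety output and would largely count responders.** It is not in the outcome lists of Sections 2 and 4.5. Many responders could never meet the limb, and withdrawing drugs at baseline may offset part of the fall.

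**Conclusion.** The point holds as a wording defect of moderate severity. The HbA1c change limb lacks a direction in all three places, and its scale is not stated. Under a literal reading, a fall of more than one point between consecutive measurements is recorded as hyperglycaemia. The 31% to 60% at week 13 is a worst case, resting on assumed means and SDs, a normal distribution and fully literal coding. It is not a forecast: if staff read the limb as a rise, no fall is miscoded.

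The conflict between footnote c and Sections 4.2.2 and 4.6 over automatic or discretionary reintroduction is a contradiction whichever direction is meant. It reaches the primary endpoint only through restarts that continue into the two-month window. The protocol offers no basis for estimating how many there would be.

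**What to change.** In the Section 5.1 adverse event definition, state the direction of the HbA1c limb so that a fall is not coded as hyperglycaemia, and state whether 1% means absolute percentage points.

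The clinical team must reconcile the reintroduction wording in Section 4.2.2, Section 4.6 and Appendix A footnote c on two matters: the direction of change meant, and whether reintroduction is mandatory or at the GP's discretion. Which rule applies is for that team to decide. The agreed text should then be used in every place and in the CRF checks.

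The cost is a few words in each place and any matching CRF check, made through the protocol's amendment procedure. If data have already been collected, hyperglycaemia records resting only on the HbA1c change limb should be checked against the paired values.

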	
 • Myocardial infarction within previous 6 months • Learning difficulties which in the opinion of the investigator prevent the subject providing informed consent and complying safely with the diet • Use of weight loss agents or medications taken to primarily reduce weight (eg orlistat, lorcaserin, Qysmia, Contrave, GLP-1 receptor analogues, over the counter or herbal weight loss agents) within the past 3 months • Have ever been diagnosed with and eating disorder or engaged in purging behaviour • Pregnant/ considering pregnancy • people currently participating in another clinical research trial • Allergy to Optifast or any of its ingredients
Product, Dose, Modes of Administration:	
The intervention is a 3400kJ (800kcal)/day TDR, followed for 13 weeks, with stepped food reintroduction to long-term weight loss maintenance using a tested energy-restricted nutritionally balanced (30% fat, < 10% saturated fat) maintenance diet using food-group exchanges, and support for behaviour change. Physical activity will be encouraged with a recommendation of at least 30 minutes brisk-walking daily and aiming to reach and maintain an individual sustainable maximum with a target of 15,000 steps/day.
 
Participants will continue to receive standard care under current clinical guidelines for T2DM. Intention to treat analysis will be conducted, with follow-up data continuing to be collected even if treatment is stopped.
 
The intervention will be delivered in primary care practices by practice nurses/dietitians (according to local availability and practice) with training, support and mentoring from the Boden Collaboration, University of Sydney.

Duration of Treatment:	12 months. Subject to additional funding, at least annual follow up for 5 years
Statistical Analysis:	
Data will be analysed primarily on an intention-to-treat (ITT) basis, using last observation carried forward for weight and diabetes status for subjects who discontinue the formal weight management program or experience an adverse event.
 
A ‘completers analysis’ of participants who complete the study will also be performed.

STUDY FLOW CHART

Screening and Baseline appointments

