4.3.5 Blood pressure –

Blood pressure will be measured while seated after 5 minute rest using either a stethoscope and sphygmomanometer or digital sphygmomanometer. The same type of equipment should be used for each participant for the duration of the study. The arm should be relaxed and resting on a table

or desk so that the participant is not supporting their own arm. The appropriate cuff size must be used to ensure accurate measurements. The upper arm should be encircled by at least 80% of the total length of the cuff. The cuff is to be applied around the upper arm so that the midpoint of the length of the cuff lies over the brachial artery and mid-height of the cuff is at heart level. The bottom of the cuff should be approximately 2 cm above the elbow crease. If measuring blood pressure manually, stethoscope will be placed over brachial artery and the cuff inflated to 160mmHg (in those with no history of hypertension) or 200mmHg (for those with a history of hypertension) and slowly deflated at 2-3mmHg. The first Korotkoff sound will be recorded for systolic blood pressure and the last Korotkoff sound will be recorded for diastolic blood pressure. Three recordings will be collected 2-3 minutes apart. The same arm will be used to measure blood pressure throughout the study. Patients will be asked about symptoms of postural hypotension and blood pressure will be measured at all appointments.

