Note: this refers to an event in which the participant was at risk of death at the time of the event. It does not refer to an event, which hypothetically might have caused death if it were more severe.

- Hospital admission or prolonged hospital admission

Note: hospitalisation for elective treatment of a pre-existing condition that did not worsen from signing of consent is not considered an AE

- Congenital abnormality
- Permanent damage or disability

Note: The term disability means a substantial disruption of a person's ability to conduct normal life functions. This definition is not intended to include experiences of relatively minor medical significance such as uncomplicated headache, nausea, vomiting, diarrhoea, influenza, and accidental trauma (e.g. sprained ankle) which may interfere or prevent everyday life functions, but do not constitute a substantial disruption

- Other important medical event

Medical and scientific judgement should be exercised in deciding whether reporting is appropriate in other situations, such as important medical events that may not be immediately life-threatening or result in death or hospitalisation, but may jeopardise the participant, or may require medical or surgical intervention to prevent one of the other outcomes listed in the above definition. These should also be considered serious. Examples of such events are invasive or

malignant cancers, intensive treatment in an emergency room or at home for allergic bronchospasm, blood dyscrasias or convulsions that do not result in hospitalisation, or the abuse of study treatments

The Adverse Events form should be completed with the question regarding seriousness (serious or not serious) answered in the affirmative. Additional information including summary of the event should be recorded in the Serious Adverse Event form. It is the responsibility of the GP/dietitian/nurse to review all documentation (e.g. hospital progress notes, laboratory, and diagnostic reports) related to the event and record all relevant information in the SAE form. The event must be followed up and new information added until the event has resolved or there is no new information

Serious adverse event reporting

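### Section 5.1 requires an adverse event to be new or worsening, but has blood pressure recorded as one by fixed cut-offs that ignore baseline

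*Protocol*

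**What the plan says.** Section 5.1 of the protocol opens with a general definition: "Adverse events are defined as any new medical event or worsening of an existing condition", subject to the condition "with onset after the signing of consent". Under a later subheading for glycaemia and blood pressure, it directs that "low and high blood pressure will be recorded as adverse events using the criteria below". The high criterion is "Systolic >140 or diastolic > 90". The low criterion is systolic below 110 or diastolic below 60. Either component alone is enough. Neither criterion mentions baseline, size of change, persistence or a history of hypertension.

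Four other places bear on this:

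- Sections 3.2 and 3.3 set no blood pressure limit at entry.
- Section 4.3.5 expects participants with known hypertension, since it gives them their own cuff-inflation pressure. It asks for three recordings at each appointment and does not say which one, or what summary of them, is the value.
- Section 4.6 and Appendix A measure blood pressure at screening (Appt 1) and at every later appointment. Adverse events are recorded from Appt 2, when the diet starts.
- Section 4.2.2 uses the same figures as prompts for reviewing blood pressure medication.

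**The concern.** The two parts of Section 5.1 do not agree. Take a participant whose usual pressure is 150/85, seen at screening and again at Appt 2. Under the general definition nothing has happened, because hypertension was there before consent and has not worsened. Under the cut-off it is an adverse event on the day the diet starts, before the diet can have had any effect. The same holds on the low side for someone whose usual pressure lies below 110 systolic or 60 diastolic.

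What is at stake is how the safety data are read. DiRECT-Aus has a single arm, so no comparison group shows how many such entries would arise anyway. A count containing unchanged, or even improved, blood pressures overstates events during the intervention. Practices may also settle the conflict differently. Dietitians and nurses may record adverse events, and they must consult the GP when unsure about relatedness or action. Nothing tells them how to decide whether a long-standing high reading is an event at all.

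**Working it through.** **Plan's own figure.** There is none to reproduce. The protocol gives no baseline blood pressure, no prevalence of hypertension and no expected event count.

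**The texts side by side**

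| Element | General definition, 5.1 | Blood pressure criteria, 5.1 |
|---|---|---|
| Baseline | new, or worse than an existing condition | not mentioned |
| Onset | after consent | not mentioned |
| Force | definition | mandatory recording |
| Pre-existing condition | outside, unless worse | no exception |

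Two features of Section 5.1 bear on whether the definition silently limits the cut-offs. First, the hyperglycaemia criterion in the same list includes a change rule (more than 1% in HbA1c since the previous measurement), while the blood pressure criteria have none. Second, the section does make an exception for conditions that have not worsened, but only for admissions: "hospitalisation for elective treatment of a pre-existing condition that did not worsen from signing of consent is not considered an AE". The authors wrote a change rule and a pre-existing-condition exception where they wanted them, and wrote neither for blood pressure.

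**Size, counted in participants**

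- N = 250 (Section 3.1).
- p = share of participants beyond the high cut-off at baseline. Assumed range 0.05 to 0.30; not in the documents.
- Participants carrying an event that is neither new nor worse = N × p.
- Low end: 250 × 0.05 = 12.5, about 12.
- High end: 250 × 0.30 = 75.

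This counts each person once and leaves out the low cut-off.

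**Are such participants the only source of crossings?** A simulation with assumed inputs says not. It took mean systolic pressure of 125 to 135, a between-person SD of 14, a within-person SD of 8, an on-study change of 0 to −10 mmHg, and one systolic value at each of the 18 appointments after baseline. A crossing is a value above 140; diastolic pressure was ignored.

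- Above 140 at baseline: 17% to 38%. As a check, the total SD is √(14² + 8²) = 16.1, so P = 1 − Φ((140 − 125)/16.1) = 0.18 and 1 − Φ((140 − 135)/16.1) = 0.38. This overlaps the assumed 5% to 30% but reaches above it.
- At least one crossing after baseline: 24% to 74% of participants.
- Of those who cross, 35% to 68% were already above 140 at baseline.

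The remainder cross from a baseline at or below 140, in part through ordinary visit-to-visit variation. These figures depend wholly on the assumed inputs.

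**The case against.** The best defence is that the cut-offs sit beneath the general definition and are limited by it: they say what counts as high or low, and the definition says when that is an adverse event. On this reading a usual 150/85 at Appt 2 is not an event. The reading is possible, so the defect is an unresolved conflict and not an express rule to ignore baseline. But the recording instruction is mandatory and has no qualifier, so site staff cannot be relied on to read it that way.

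It can also be said that over-capture tied to medication-review prompts is a reasonable safety choice, and that tabulation belongs in the SAP, which is not at hand. Both are fair. Neither removes the conflict, because the protocol itself fixes the definition and the recording rule.

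A reader might infer three stronger things that the documents do not support:

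- *Every later high visit adds another event.* Each adverse event record has a start date, an end date and a status that includes not resolved, and the term should be a diagnosis. That structure suits one open episode, so multiplying a rate by the number of appointments counts visits, not events.
- *Pre-existing hypertension dominates the safety results.* No expected number of other events is given, so dominance cannot be judged.
- *A blood pressure event replaces outcome data.* The Synopsis applies last observation carried forward to subjects who "discontinue the formal weight management program or experience an adverse event". Section 6 limits it to those who discontinue the program, and Section 3.5 uses the best available follow-up weights and end-of-study diabetes status. The Synopsis wording is a separate inconsistency that touches every kind of adverse event; the blood pressure cut-offs neither cause nor cure it.

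**Conclusion.** The point holds as an internal inconsistency in Section 5.1. Read literally, the cut-offs turn stable blood pressure already beyond a limit into an on-study adverse event, which the section's own definition excludes. The effect is to overstate events in a study without a control arm, and probably to make recording uneven between practices. Its size cannot be derived from the documents. About 12 to 75 of 250 participants follows from an assumed 5% to 30% beyond the high cut-off at baseline, counted once each. No effect on the remission endpoint is shown. Whether the cut-offs are clinically right is not in question here.

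**What to change.** Reconcile the two texts in Section 5.1, for example:

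*A blood pressure value beyond a cut-off in this section is reported as an adverse event only if it is new, or worse, relative to the participant's screening and baseline readings. Consecutive values beyond the cut-off form one event with one start date and one end date.*

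The protocol should define what counts as worse, and should say which of the three recordings, or which summary of them, is compared with the cut-off. All raw crossings should be tabulated by visit, apart from adverse events, with the proportion beyond each cut-off at baseline alongside. First crossings by people within the limits at baseline will still be events, and the baseline column helps the reader judge them.

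The cost is wording, plus a flag derived from readings already collected. Some unchanged readings leave the event listing but stay in the by-visit table. The cut-offs and the medication-review rules in Section 4.2.2 are not altered.
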